Study Protocol

Protocol ID: 2025ZSLYEC-747

Title: Exploring the Clinical Value of an AI-Assisted Patient Self-Assessment App for Bowel

Preparation: A Multicenter Study

Document date: 9,1, 2025

Background and aim

Colonoscopy is a key tool for screening, diagnosing and treating colorectal cancer. Early detection and removal of polyps can substantially reduce both the clinical burden and the economic cost of advanced-stage disease. Adenoma detection rate (ADR)—the proportion of colonoscopies in which at least one adenoma is found—is the principal quality indicator; every 1 % drop in ADR increases subsequent cancer risk by 3 %. Adequate bowel preparation improves ADR, cuts the miss rate for polyps and cancers, and lowers post-colonoscopy cancer incidence, whereas poor preparation decreases polyp/ tumour detection, prolongs insertion time, increases endoscopist fatigue and may raise procedure-related complications. Yet 20–25 % of examinations are still performed under sub-optimal conditions.

The quality of cleansing depends largely on patient compliance with the purgative regimen, so intensive education is essential. Telephone calls, text messages, short videos and mini-programs have all been shown to improve compliance and preparation quality. However, early identification of individuals who are likely to prep poorly—and the opportunity to rescue them—remains an unmet need. The character of the last stool after laxative intake correlates closely with overall preparation quality; staff often ask patients to describe this stool to decide whether to proceed or delay the examination, but this is reactive rather than proactive. Allowing patients to self-assess and, if necessary, present early (out-patients) or alert staff (in-patients) for rescue could convert sub-optimal into adequate preparation.

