After taking the bowel-prep solution, patients in the app group are instructed to photograph their final stool in the toilet and upload the image through our smartphone app. The AI algorithm immediately scores the prep quality. If the image is rated “poor” or “inadequate,” the app displays an alert advising the patient to come to the hospital early or contact clinical staff; clinical staffs then review the photo and decide whether a rescue preparation is needed. The standard rescue was an additional packet of polyethylene glycol. If the image is rated “adequate,” the patient is told the prep is acceptable and should proceed to the appointment, where clinical staffs will use the uploaded photo to confirm eligibility for colonoscopy.

The control group followed the conventional procedure: before the examination, clinical staffs asked questions and relied on the patient’s verbal description of their stool to judge the adequacy

of bowel preparation. If the prep was deemed inadequate, the standard rescue was an additional packet of polyethylene glycol.

Outcome parameters

The primary outcome parameter is the comparison of the bowel preparation quality between the app group and the control group (the rate of adequate and excellent bowel preparation).

The secondary outcome parameters are:

cecal intubation rate

cecal intubation time

withdrawal time (excluding polypectomy and biopsy)

polyp-detection rate (PDR)

adenoma-detection rate (ADR)

advanced-adenoma-detection rate (aADR)

use of rescue preparation

rate of rescheduled examinations due to inadequate preparation

clinical staffs' assessment time

user satisfaction score,

and post-procedural adverse events.

The results will be analyzed in full analysis set, per-protocol set and safety set.

Sample Size

Assuming that 16 % of patients have inadequate bowel preparation with the traditional regimen, and the app is expected to convert 25 % of these failures (i.e., 4 % of the total cohort) to adequate preparation, a sample size of 235 participants is required for $\alpha = 0.05$ and power = 0.80.

Allowing for a 10 % dropout rate, we plan to enroll 262 subjects per arm, for a total of 524 participants.

Randomization

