Stratified randomization by center. Random numbers generated in Excel by an independent statistician; sequentially numbered, sealed, opaque envelopes prepared and held by the third party. The envelopes constitute the allocation sequence; random numbers remain concealed from patients and endoscopists until the envelope is opened immediately before allocation.

Blinding

Patients cannot be blinded; operators, outcomes assessors, and pathologists will remain blinded.

Statistical analysis

All analyses were performed with SPSS version 26. Baseline characteristics were examined to assess balance across concentration groups. Normally distributed continuous variables are presented as mean \pm SD and compared between groups using independent-samples t-tests; non-normally distributed continuous variables are expressed as median (interquartile range) and compared with the Wilcoxon rank-sum test. Categorical rates were compared using the χ^2 test. A two-sided $P < 0.05$ was considered statistically significant.

References

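### Baseline data serve only a balance check and every rate goes to an unadjusted χ² test: valid, but it gives up a small amount of precision that a prespecified adjusted risk difference would recover

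*Protocol*

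**What the plan says.** In the protocol's Statistical analysis section, baseline data appear once: "Baseline characteristics were examined to assess balance across concentration groups". The tests follow. For rates: "Categorical rates were compared using the χ^2 test". Normally distributed continuous outcomes are "compared between groups using independent-samples t-tests", and the others go to a Wilcoxon rank-sum test. No adjusted estimate is named.

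The Randomization section states "Stratified randomization by center"; the Methods section lists five sites. The primary outcome is "the rate of adequate and excellent bowel preparation". PDR, ADR and the advanced-adenoma-detection rate (aADR) are secondary.

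The protocol does not list its baseline variables. Age appears as an entry criterion. In-/out-patient status appears only in Background and aim, where patients would "present early (out-patients) or alert staff (in-patients) for rescue". Sex is not mentioned.

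**The concern.** A balance check after randomisation corrects nothing if no adjusted analysis follows. The sentence describing it also names comparison groups that this trial does not have; it looks like text carried over from another study and has to be corrected in any case.

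Age and sex plausibly predict polyps and adenomas, and care setting plausibly predicts preparation quality. A prespecified adjusted risk difference would use that information and narrow the interval while keeping type I error at its nominal level. Leaving out centre also means that the analysis does not follow the randomisation. At stake is a modest amount of precision in the preparation, PDR and ADR comparisons.

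**Working it through.** **Inputs from the protocol.** Inadequate preparation 16% in controls; a quarter of failures converted, hence 12% with the app; two-sided α 0.05; power 0.80; 235 before dropout, read as per arm because 262 per arm follows from it (235/0.9 = 261.1, rounded up to 262). Pilot inadequate rates: 10% versus 3%.

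**Assumed inputs, because the protocol gives none.**
- Preparation: 20-50% in-patients; inadequate preparation 22-30% in in-patients and 12-14% in out-patients.
- ADR: 20-30%; odds ratio 1.3-1.7 per 10 years of age and 1.5-2.0 for male sex; age roughly normal (mean 52, SD 13, cut to 18-85); half of the patients male.

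**1. The plan's own figure.** The two-sided pooled two-proportion formula for 16% versus 12% gives 1181 per arm, not 235. Power at 235 per arm is 23.8%. This is the starting point against which any gain has to be seen.

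**2. Variance explained, preparation rate.** With a share f of in-patients, R² = f(1−f)(p_in − p_out)² / [p(1−p)]. Hold the overall rate p at the planned 16%, so that f = (0.16 − p_out)/(p_in − p_out):
- p_out 14%, p_in 22%: f = 0.25; R² = 0.1875 × 0.0064 / 0.1344 = 0.009.
- p_out 12%, p_in 22%: f = 0.40; R² = 0.24 × 0.0100 / 0.1344 = 0.018.
- p_out 12%, p_in 30%: f = 0.222; R² = 0.1728 × 0.0324 / 0.1344 = 0.042.

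Half in-patients with 30% versus 12% would give 0.049, but that implies 21% inadequate overall, above the plan's 16%. The usable range is therefore about 1-4%. It covers the adequate-preparation rate only; no figure was derived for the excellent-preparation rate.

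**3. Variance explained, ADR.** R² = Var(p(x)) / [p(1−p)] over a large simulated population of age and sex:
- ADR 20%, odds ratios 1.3 and 1.5: 0.023.
- ADR 30%, odds ratios 1.7 and 2.0: 0.099.

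**4. What that is worth.** The standard error is multiplied by √(1−R²), which is equivalent to a sample of 235/(1−R²) per arm.

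| Outcome | R² | SE reduction | Equivalent extra patients per arm |
|---|---|---|---|
| Preparation, low | 0.009 | 0.5% | 2 |
| Preparation, high | 0.042 | 2.1% | 10 |
| ADR, low | 0.023 | 1.2% | 6 |
| ADR, high | 0.099 | 5.1% | 26 |

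Power for 16% versus 12% at 235 per arm goes from 23.8% to 24.0% (R² 0.009) or 24.7% (R² 0.042). At the pilot rates it goes from 87.1% to 87.4% or 88.4%. For an illustrative ADR of 25% versus 30%, it goes from 22.7% to 24.8% at R² 0.10. Reaching 80% power for 16% versus 12% would need R² = 1 − 235/1181 = 0.80.

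**5. Type I error.** In 2,000 simulated null trials (235 per arm, ADR 30%), a linear model with robust standard errors rejected 4.7% of the time, and the variance of the risk difference fell by 9.8%.

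**6. How many covariates the data support.** Inadequate preparations expected at 235 per arm: 235 × (0.16 + 0.12) = 66. At the pilot rates: 235 × (0.10 + 0.03) = 31. Arm, four centre indicators, age and care setting make seven terms: 66/7 ≈ 9 failures per term, but only 31/7 ≈ 4 at the pilot rates.

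**The case against.** The strongest reply is that nothing here is an error. A reader might infer that the unadjusted comparison is biased, or that chance imbalance invalidates it. The protocol does not support that: under randomisation the χ² test is valid, and its error rate and interval already allow for chance imbalance. This stands.

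It can also be said that covariate choice belongs in the statistical analysis plan, which is not shown. That stands in part. But the protocol does not leave the method open: it names an unadjusted test for every rate, and a later plan with an adjusted main analysis would depart from it.

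A reader might further infer that adjustment is free and that the covariates are in hand. Neither is documented. Only age is tied to entry, no prognostic strength is stated, and covariates have to be recorded and fixed in advance. Nor would adjustment let this trial separate detection rates that the pilot could not, as the small change in ADR power shows.

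Finally, adjusting for patient characteristics while omitting centre would still not match the randomisation. That is right, and centre belongs in the model. A plain logistic odds ratio would not serve either: it targets a conditional effect, and its standard error does not shrink. The gain requires a marginal risk difference.

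**Conclusion.** The point holds as an optional improvement in efficiency, together with a wording error that must be corrected. The stated analysis is valid, but it ignores centre and any prognostic baseline value. Under the assumed strengths, the loss is about 1-4% of the variance for the adequate-preparation rate and about 2-10% for ADR. Both ranges are assumptions and would change with the true in-patient share, age spread and odds ratios. On the protocol's own effect, the gain for preparation is less than one percentage point of power. It has no bearing on the gap between 235 and 1181 per arm, which is a separate and much larger problem.

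**What to change.** - Make the main comparison of the preparation rates, PDR and ADR a prespecified adjusted risk difference with 95% CI, from logistic regression with standardisation or a linear model with robust standard errors.
- Include centre and age in each model. Add sex for PDR and ADR, and in-/out-patient status for preparation, where these are recorded at baseline. State in the protocol which of them are recorded.
- Keep the covariates few for aADR, which has fewer events than ADR. State in advance a reduced model for preparation in case failures are as rare as in the pilot.
- Keep χ² as a supportive analysis.
- Correct the baseline sentence to app versus control, make the table descriptive, and do not choose covariates from observed imbalance.

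The cost is a few sentences of protocol text, slightly more analysis work, and the need to record and prespecify the covariates. No additional patients are needed.

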Artificial intelligence is now widely used in gastrointestinal endoscopy. In our pilot work we developed a smartphone app that uses AI to grade stool photographs. In an internal validation set the algorithm achieved 100 % sensitivity (95 % CI 34.2–100 %) and 94.1 % specificity (90.1–96.5 %) for binary classification of adequacy. We then conducted a single-centre RCT; 461 patients (229 control, 232 app) were analysed. App users had significantly higher adequate-preparation rates (97 % vs 90 %, $P = 0.002$) and excellent-preparation rates (86.2 % vs 59.8 %, $P < 0.001$), and higher mean Boston Bowel Preparation Scale (BBPS) scores (8.2 ± 0.8 vs 7.8 ± 1.2 , $P < 0.001$) as well as segment-specific BBPS sub-scores. Cecal intubation rate, polyp-detection rate (PDR) and ADR did not differ between groups. These findings suggest the app improves preparation quality, but the single-centre design limits generalisability. We now propose a multicentre study to confirm the clinical value of this AI-assisted self-assessment tool.

Methods

Study design: a multicenter, randomized controlled clinical trial.

Location: The Sixth Affiliated Hospital, Sun Yat-sen University; Tianjin Haihe Hospital

Guangdong Second Provincial General Hospital

Dongguan Humen Hospital of Traditional Chinese Medicine

Cangzhou Central Hospital

The inclusion criteria:

- (1) Age ≥ 18 years
- (2) Undergoing colonoscopy at a participating site
- (3) Able to defecate in a toilet (or in a setting where stool characteristics can be observed) after taking the bowel-prep solution
- (4) Proficient in using a smartphone
- (5) Willing to participate voluntarily

The exclusion criteria:

- ① American Society of Anesthesiologists (ASA) class III or IV;
- ② Gastric-outlet or intestinal obstruction;
- ③ Active gastrointestinal bleeding;
- ④ Enterostomy (colostomy/ileostomy);
- ⑤ Status post total colectomy.

Intervention

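### Randomisation is stratified by centre, but the only test named for the primary rates ignores centre; stratifying that test is a cheap change with a small gain

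*Protocol*

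**What the plan says.** - Protocol, Methods: a multicentre randomised trial at five listed hospitals. Background and aim says of the pilot RCT that "the single-centre design limits generalisability", and gives this as the reason for a multicentre study.
- Protocol, Randomization: "Stratified randomization by center". Centre is the only stratification factor. Blocking and block size are not stated.
- Protocol, Outcome parameters: the primary comparison is on "the rate of adequate and excellent bowel preparation", read here as two rates.
- Protocol, Statistical analysis: "Categorical rates were compared using the χ^2 test", and "A two-sided $P < 0.05$ was considered statistically significant". Continuous variables get the t-test or the Wilcoxon rank-sum test. There is no stratified test, centre term, regression model or by-centre display.
- Protocol, Sample Size: 16% inadequate preparation in the control arm; "the app is expected to convert 25 % of these failures", stated to be 4% of the cohort. "Allowing for a 10 % dropout rate, we plan to enroll 262 subjects per arm".

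**The concern.** A primary analysis normally respects the factor used to stratify randomisation, because that is the comparison the design sets up. Here the protocol names its test, and the test drops centre. If preparation quality differs between hospitals, between-centre variation stays in the error term of the plain test. With balanced allocation within centre the test then becomes somewhat conservative. Without balance, chance differences in centre mix between the arms add noise.

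Two further points follow. The stated reason for the trial is to go beyond one centre, yet nothing in the analysis text would show whether the result is consistent across centres. Also, a plain and a stratified test can fall on opposite sides of 0.05 in a borderline trial, so the preferred one should be settled before data are seen. What is at stake is a little precision and clarity, not validity.

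**Working it through.** **Inputs from the protocol.** Control 84% adequate (16% inadequate). App 88% adequate: 0.16 × 0.25 = 0.04, so 12% inadequate. Two-sided alpha 0.05; 235 evaluable and 262 enrolled per arm; five centres. Pilot excellent-preparation rates 59.8% (control) and 86.2% (app).

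**Inputs assumed.** Centre sizes, centre rates and block sizes are not given. The main setting uses unequal centres of 179/99/81/63/48 patients (total 470) and three spreads of control rates, each averaging 84%:
- wide: 0.850/0.716/0.972/0.764/0.935
- mild: 0.844/0.766/0.922/0.805/0.883
- none: 0.84 in every centre

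The app rate in each centre is control + 0.25 × (1 − control), so the overall difference is 4.0 points.

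**Step 1: the plan's own figure.** The dropout step reproduces: 235/0.9 = 261.1, rounded up to 262, and 2 × 262 = 524. The 235 does not. The pooled two-proportion formula gives

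n = [1.960 √(2 × 0.14 × 0.86) + 0.842 √(0.16 × 0.84 + 0.12 × 0.88)]² / 0.04² = (0.962 + 0.412)² / 0.0016, about 1,181 per arm.

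Exact power of the plain test is 24.0% at 235 per arm and 26.4% at 262. This is a separate problem. It matters here only as the baseline for the comparison below.

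**Step 2: the two tests.**
- Plain chi-square: the squared difference in overall rates divided by p(1 − p)(1/n₁ + 1/n₀), with p the overall rate.
- CMH, without continuity correction: in centre k with n₁ₖ app and n₀ₖ control patients (Nₖ in all), aₖ adequate in the app arm and mₖ adequate in total, Eₖ = n₁ₖmₖ/Nₖ and Vₖ = n₁ₖn₀ₖmₖ(Nₖ − mₖ)/[Nₖ²(Nₖ − 1)]. The statistic is [Σ(aₖ − Eₖ)]²/ΣVₖ.

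Both are referred to chi-square with 1 df.

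**Step 3: how much variance lies between centres.** With the wide spread, averaging the arms, the pooled variance is 0.86 × 0.14 = 0.1204 and the size-weighted within-centre variance is 0.1143. The ratio is 0.1204/0.1143 = 1.053. Over equal and unequal centres the ratio is 1.053 to 1.070 (wide) and 1.017 to 1.021 (mild), worth about 8 to 31 of 470 patients.

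**Step 4: simulation, adequate rate, 200,000 trials per setting.**

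| Spread | Balanced within centre | Chi-square power | CMH power |
|---|---|---|---|
| Wide | yes | 23.3% | 24.9% |
| Wide | no | 23.9% | 24.7% |
| Mild | yes | 23.8% | 24.2% |
| Mild | no | 23.7% | 23.9% |
| None | yes | 24.1% | 24.0% |
| None | no | 24.0% | 23.8% |

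Over all settings (470 or 524 patients, equal or unequal centres) the change in power from stratifying runs from −0.3 to +2.0 points.

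Type I error of the plain test is 4.2–4.4% (wide) and 4.7–4.9% (mild) with balance, and 5.0–5.1% otherwise. CMH stays at 4.9–5.0%.

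Under the planned effect, the tests disagree on significance in 1.4–2.0% of trials (wide, balanced) and 6.1–7.2% (wide, not balanced). At mild spread, unequal centres, the figures are 0.6% and 3.9%.

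A separate run with a common odds ratio, exact balance and equal centres gave the same picture: 23.9% against 23.8% with no spread, and 22.9% against 25.4% with control rates of 66–96%.

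**Step 5: excellent rate.** The protocol gives no planning effect. Assuming control 59.8% and 25% conversion (59.8 + 0.25 × 40.2 = 69.9%), the change runs from −0.5 to +3.0 points. The top end needs equal centres with control rates of 40–80% (63.0% against 66.0%). At the pilot's 59.8% against 86.2%, both tests have about 100% power.

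**Step 6: is CMH usable with few failures?** Expected inadequate preparations: 235 × 0.16 + 235 × 0.12 = 37.6 + 28.2, about 66. The Mantel-Fleiss value is about 33, against a requirement of more than 5.

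**The case against.** The strongest reply is that nothing here is an error. The chi-square test holds its level, the gain is a point or two of power at best, and the visible part of it comes from a wide spread that is assumed. At mild spread it is a few tenths of a point, and with no spread CMH is very slightly worse. The chi-square sentence is also a generic rule by variable type, and the handling of stratification factors is often left to the SAP. All of this is fair and keeps the point minor. But the protocol does not leave the primary test open: it names one, and that one ignores the only stratification factor. If an SAP names a stratified test, the two texts need aligning.

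Two narrower replies stand in part:
- The protocol has already fixed a test in advance, and two valid tests disagree now and then anyway: about 2.2% of trials with no centre difference and unbalanced allocation. Disagreement is therefore a reason to choose deliberately now. It is not evidence against chi-square.
- CMH yields one pooled comparison and does not show consistency across centres. Only the by-centre rates do that.

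**Conclusion.** The point holds as a low-severity improvement. The named primary test omits the randomisation stratum. Stratifying it moves power for the adequate rate by −0.3 to +2.0 points over the main assumed settings, and by about 2.5 points at the widest spread tried. It also brings type I error back to about 5% where the plain test is mildly conservative. The size depends wholly on centre sizes, centre rates and within-centre balance, none of which the protocol gives; if centres do not differ, there is nothing to gain. The plain test is not invalid. The change does nothing material for the sample-size shortfall, which needs its own correction.

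**What to change.** Before data are seen, replace the chi-square sentence in Statistical analysis with wording such as:

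> The primary rates (adequate and excellent preparation) are compared with the Cochran-Mantel-Haenszel test stratified by centre, without continuity correction. Rates by arm are shown for each centre. Secondary categorical rates are compared using the chi-square test.

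Reporting the Mantel-Haenszel risk difference with a 95% CI, and keeping the unstratified chi-square test as a sensitivity analysis, are useful additions but not essential. If the risk difference is added, confirm that the named software produces it. If an SAP already specifies a centre-stratified primary test, align this sentence with it. The wording does not settle whether one or both primary rates must succeed; that has to be stated separately.

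The cost is a few sentences of analysis text, with no new data, patients or visits. If centres turn out not to differ, the loss is at most about 0.5 points of power.
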